8.3. Adverse Events, Serious Adverse Events, and Product Complaints

The definitions of the following events can be found in Appendix 3 (Section 10.3):

- AEs
- SAEs
- Product complaints (PCs).

These events will be reported by the participant (or, when appropriate, by a caregiver, surrogate, or the participant's legally authorized representative).

The investigator and any qualified designees are responsible for detecting, documenting, and recording events that meet these definitions and remain responsible for following up events that are serious, considered related to the study intervention or study procedures, or that caused the participant to discontinue the study (see Section 7).

Care will be taken not to introduce bias when detecting events. Open-ended and non-leading verbal questioning of the participant is the preferred method to inquire about event occurrences.

After the initial report, the investigator is required to proactively follow each participant at subsequent visits/contacts. All SAEs will be followed until resolution, stabilization, the event is otherwise explained, or the participant is lost to follow-up (as defined in Section 7.3). For PCs, the investigator is responsible for ensuring that follow-up includes any supplemental investigations as indicated to elucidate the nature and/or causality. Further information on follow-up procedures is provided in Section 10.3.

8.3.1. Timing and Mechanism for Collecting Events

This table describes the timing, deadlines, and mechanism for collecting events.

Event	Collection Start	Collection Stop	Timing for Reporting to the Sponsor or Designee	Mechanism for Reporting	Back-up Method of Reporting
Adverse Event					
AE	Signing of the ICF	Participation in study has ended	As soon as possible upon site awareness	AE eCRF	N/A
Serious Adverse Event					
SAE and SAE updates – prior to start of study intervention and deemed reasonably possibly related with study procedures	Signing of the ICF	Start of intervention	Within 24 hours of awareness	SAE paper form	SAE paper form
SAE and SAE updates – after start of study intervention	Start of intervention	Participation in study has ended	Within 24 hours of awareness	SAE paper form	SAE paper form

Event	Collection Start	Collection Stop	Timing for Reporting to the Sponsor or Designee	Mechanism for Reporting	Back-up Method of Reporting
SAE – after participant's study participation has ended and the investigator becomes aware	After participant's study participation has ended	N/A	Promptly	SAE paper form	N/A
Pregnancy					
Pregnancy in female participants and female partners of male participants	After the start of study intervention	84 days postdose (Day 85)	Within 24 hours of learning of the pregnancy	Pregnancy paper form	SAE paper form
Product Complaints					
PC associated with an SAE or might have led to an SAE	Start of study intervention	End of study intervention	Within 24 hours of awareness	Product Complaint form	N/A
PC not associated with an SAE	Start of study intervention	End of study intervention	Within 1 business day of awareness	Product Complaint form	N/A
Updated PC information	—	—	As soon as possible upon site awareness	Originally completed Product Complaint form with all changes signed and dated by the investigator	N/A
PC (if investigator becomes aware)	Participation in study has ended	N/A	Promptly	Product Complaint form	

Abbreviations: AE = adverse event; eCRF = electronic case report form; ICF = informed consent form; PC = product complaint; SAE = serious adverse event

8.3.2. Adverse Events of Special Interest

The following AEs of special interest will be used to determine the safety and tolerability of mirikizumab administered through PFS or AI in this clinical study:

- infection
- systemic allergic/hypersensitivity reactions.

If infections or allergic/hypersensitivity reactions are reported, site staff will provide details on these events as instructed on the eCRF. A PK, immunogenicity, and hypersensitivity cytokine panel (Appendix 7, Section 10.7) will be collected when possible for any participant who experiences an AE of systemic allergic/hypersensitivity reaction during the study.

8.4. Treatment of Overdose

For this study, any dose of mirikizumab greater than the intended dose of 300 mg will be considered an overdose.

The sponsor does not recommend specific treatment for an overdose.

In the event of an overdose, the investigator should:

1. Contact the medical monitor immediately.
2. Closely monitor the participant for any AE/SAE and laboratory abnormalities until no longer has a clinical effect or can no longer be detected systemically at least 84 days postdose (Day 85). Refer to Section 8.3 for reporting details.
3. Document the quantity of the excess dose as well as the duration of the overdose in the eCRF.

Decisions regarding dose interruptions or modifications will be made by the investigator in consultation with the medical monitor based on the clinical evaluation of the participant.

8.5. Pharmacokinetics

Blood samples of approximately 3 mL will be collected for measurement of serum concentrations of mirikizumab as specified in the SoA (Section 1.3).

A maximum of 3 samples may be collected at additional time points during the study if warranted and agreed upon between the investigator and the sponsor. The timing of sampling may be altered during the course of the study based on newly available data (e.g., to obtain data closer to the time of peak serum concentrations) to ensure appropriate monitoring.

Instructions for the collection and handling of biological samples will be provided by the sponsor. The actual date and time (24-hour clock time) of each sample will be recorded.

8.5.1. Bioanalysis

Samples will be analyzed at a laboratory approved by the sponsor and stored at a facility designated by the sponsor.

Concentrations of mirikizumab will be assayed using a validated enzyme-linked immunosorbent assay method.

Bioanalytical samples collected to measure mirikizumab concentrations will be retained for a maximum of 1 year following the last participant visit for the study. During this time, samples remaining after the bioanalyses may be used for exploratory analyses such as metabolism work, protein binding, and/or bioanalytical method cross-validation.

8.6. Pharmacodynamics

Pharmacodynamic parameters are not evaluated in this study.

8.7. Genetics

A blood sample for DNA isolation will be collected from participants as specified in the SoA (Section 1.3).

See Appendix 5 (Section 10.5) for information regarding genetic research.

8.8. Biomarkers

Biomarkers are not evaluated in this study.

8.9. Immunogenicity Assessments

At the visits and times specified in the SoA (Section 1.3), venous blood samples of approximately 10 mL each will be collected to determine antibody production against mirikizumab. To interpret the results of immunogenicity, venous blood samples will be collected at the same time points to determine the serum concentrations of mirikizumab. Instructions for the collection and handling of blood samples will be provided by the sponsor. The actual date and time (24-hour clock time) of each sampling will be recorded.

Treatment-emergent ADAs are defined in Section 2.2.3.

Immunogenicity will be assessed using a validated assay designed to detect ADAs in the presence of mirikizumab at a laboratory approved by the sponsor. Antibodies will be evaluated for their ability to neutralize the activity of mirikizumab.

Samples will be retained for a maximum of 15 years after the last participant visit, or for a shorter period if local regulations and institutional review boards (IRBs)/independent ethics committees (IECs) allow, at a facility selected by the sponsor. The duration allows the sponsor to respond to future regulatory requests related to mirikizumab. Any samples remaining after 15 years will be destroyed.

8.10. Health Economics

This section is not applicable for this study.

9. Statistical Considerations

The statistical analysis plan (SAP) will be finalized prior to first participant first visit and it will include a more technical and detailed description of the statistical analyses described in this section. This section is a summary of the planned statistical analyses of the most important endpoints including primary and key secondary endpoints.

9.1. Statistical Hypotheses

The primary objective of this study is to evaluate PK following administration using PFS and AI.

9.2. Analyses Sets

For the purposes of analysis, the following populations are defined:

Population	Description
Enrolled	All participants randomly assigned to study intervention.
Safety	All participants randomly assigned to study intervention and who receive study intervention. Participants will be analyzed according to the intervention they actually received.
Pharmacokinetic Analysis	All enrolled participants who receive a full dose of study intervention and have evaluable PK data.

9.3. Statistical Analyses

Statistical analysis of this study will be the responsibility of the sponsor or its designee.

Pharmacokinetic analyses will be conducted on data from all participants who receive at least a full dose of the investigational product and have evaluable PK data.

Safety analyses will be conducted for all enrolled participants who received study intervention, whether or not they completed all protocol requirements.

Additional exploratory analyses of the data will be conducted as deemed appropriate. Study results may be pooled with the results of other studies for safety and population PK analysis purposes to avoid issues with post-hoc analyses and incomplete disclosures of analyses.

9.3.1. General Considerations

Data listings will be provided for all data that are databased. Data listings will be provided for all participants up to the point of withdrawal, with any participants excluded from the relevant population highlighted.

Summary statistics and statistical analysis will only be presented for data where detailed in the SAP. Summary statistics and statistical analyses will generally only be performed for participants included in the relevant analysis population. For the calculation of summary statistics and statistical analysis, unrounded data will be used.

9.3.2. Pharmacokinetic Analyses

9.3.2.1. Pharmacokinetic Parameter Estimation

Pharmacokinetic parameter estimates for mirikizumab will be calculated using standard noncompartmental methods of analysis.

The primary parameters for analysis will be the C_{max} , $AUC(0-\infty)$, and AUC from time zero to time t , where t is the last time point with a measurable concentration ($AUC[0-t_{last}]$) of mirikizumab. The secondary parameter for analysis will be the t_{max} of mirikizumab. Other noncompartmental parameters, such as half-life associated with the terminal rate constant ($t_{1/2}$), apparent total body clearance of drug calculated after extra-vascular administration (CL/F), and apparent volume of distribution during the terminal phase after extra-vascular administration (Vz/F), may be reported. Weight-normalized PK parameter estimates may be explored if deemed appropriate.

9.3.2.2. Pharmacokinetic Statistical Inference

The C_{max} , $AUC(0-\infty)$, and $AUC(0-t_{last})$ will be log-transformed and analyzed using a linear fixed-effects model. The model will include delivery device, injection location, and weight stratification as fixed-effects. The dosing regimen differences between AI and PFS administrations will be back-transformed to present the ratios of geometric LS means and the corresponding 90% CI. Comparisons will be made between the 2 delivery devices and then between the 3 injection locations.

The 2 delivery devices will be considered bioequivalent if the 90% CIs of the ratio of geometric LS means fall within 0.8 to 1.25.

The t_{max} of mirikizumab between AI and PFS administrations will be analyzed using a Wilcoxon rank sum test. Estimates of the median difference, 90% CIs, and p-values from the Wilcoxon rank sum test will be calculated.

Additional PK analyses may be conducted if deemed appropriate.

9.3.3. Safety Analyses

9.3.3.1. Clinical Evaluation of Safety

All study intervention and protocol procedure AEs and PCs will be listed, and, if the frequency of events allows, safety data will be summarized using descriptive methodology.

The incidence of symptoms for each treatment will be presented by severity and by association with study intervention as perceived by the investigator. Symptoms reported to occur prior to study entry will be distinguished from those reported as new or increased in severity during the study. Each symptom will be classified by the most suitable term from the medical regulatory dictionary.

The number of study intervention- and device-related SAEs and any related PCs will be reported.

9.3.3.2. Statistical Evaluation of Safety

Safety parameters that will be assessed include clinical laboratory parameters and vital signs. The parameters and changes from baseline (predose), where appropriate, will be listed and summarized using standard descriptive statistics. Additional analyses will be performed if warranted upon review of the data.

9.3.4. Other Analyses

9.3.4.1. Injection-site Assessments

If available, any incidence of erythema, induration, pain, pruritus, edema, bleeding, and bruising will be listed.

9.3.4.2. Evaluation of Immunogenicity

Results from immunogenicity testing will be listed. The frequency and percentage of participants with preexisting ADAs and with TE-ADAs that are positive (TE-ADA+) to mirikizumab will be tabulated. Treatment-emergent ADAs are defined as those with a titer 2-fold (1 dilution) or greater than the minimum required dilution if no ADAs were detected at baseline (treatment-induced ADA) or those with a 4-fold or greater (2 dilutions) increase in titer compared to baseline if ADAs were detected at baseline (treatment-boosted ADA). For the TE-ADA+ participants, the distribution of maximum titers will be described. The frequency of neutralizing antibodies will also be tabulated in TE-ADA+ participants.

The relationship between the presence of antibodies and PK and safety parameters of mirikizumab may be assessed.

9.4. Interim Analysis

No interim analysis is planned.

9.5. Sample Size Determination

Up to approximately 240 participants may be enrolled so that approximately 216 participants (108 in the PFS [reference] group and 108 in the AI [test] group) complete the study.

A sample size of 108 participants per treatment group will provide approximately 90% power that the 90% CI of the geometric mean ratio of C_{max} and AUC between groups will fall within equivalence range of 0.8 to 1.25. This sample size calculation was based on the assumptions that the PK parameters have log-normal distribution, the percent coefficient of variation (CV) of C_{max} and AUC are approximately 40% (based on previous trials), the expected ratio of geometric means is 1.07, and the percent CV are the same for participants from each treatment group.

Participants who are randomized but not administered treatment and participants who do not complete PK sampling through Day 85 may be replaced to ensure that approximately 216 participants (108 in each group) complete the study.

10. Supporting Documentation and Operational Considerations

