4.2. Scientific Rationale for Study Design

CCI

population of healthy participants is frequently used in the assessment of the PK of both small and large molecules.

Single 300-mg doses of mirikizumab and the PK sampling time points have been selected to generate PK profiles sufficient to fulfill the study objectives.

Participants will be randomized to receive injections in the arm, thigh, or abdomen, as injection location has been observed to have an impact on bioavailability in some studies with mirikizumab.

Previous population PK analyses have shown that patients with a lower body weight tended to have a lower clearance and/or central volume of distribution. While the effects of body weight on

these PK parameters were statistically significant, it was not considered to be clinically relevant. However, to mitigate these potentially confounding effects, approximately equal numbers of participants in each weight category are proposed to avoid a large difference in mean weight between the test and the reference delivery-device groups. A participant population of 72 per weight group is an approximate target with the recommended weight categories selected based on the distribution of weights in prior studies. The number of participants assigned to each delivery device and the number of participants assigned to each site of injection is desired to be balanced.

A parallel-group design is chosen because mirikizumab has a half-life of approximately 10 days. Additionally, a crossover study could confound PK data if participants develop neutralizing antidrug antibodies (ADAs).

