#### **9.3.2 Pharmacokinetic Statistical Methodology**

The  $C_{\max}$ ,  $\text{AUC}(0-\infty)$ , and  $\text{AUC}(0-t_{\text{last}})$  will be log-transformed and analyzed using a linear fixed-effects model. The model will include delivery device, injection location, and weight

stratification as fixed-effects. The dosing regimen differences between the AI (Test) and PFS (Reference) administrations will be back-transformed to present the ratios of geometric least squares means and the corresponding 90% CI.

Example SAS Code:

```
proc mixed data=xxx;
by parameter;
class device location strat_weight;
model log_pk = device location strat_weight / residual;
lsmeans device / alpha=0.1 cl pdiff;
ods output lsmeans=lsmeans diffs=diffs;
run;
```

The  $t_{max}$  of mirikizumab between the AI (Test) and PFS (Reference) administrations will be analyzed using a Wilcoxon rank sum test. Estimates of the median difference, 90% CIs, and p-values from the Wilcoxon rank sum test will be calculated.

Additional comparisons will be made between:

- The 2 delivery devices (AI [Test] versus PFS [Reference]) separately at each injection location (injection location will be removed from the model above)
- The 3 injection locations (arm [Test] versus abdomen [Reference] and thigh [Test] versus abdomen [Reference]) separately for each device (device will be removed from the model above)

The 2 delivery devices (AI [Test] versus PFS [Reference]) will be considered bioequivalent if the 90% CIs of the ratio of geometric least squares means of  $C_{max}$ ,  $AUC(0-\infty)$ , and  $AUC(0-t_{last})$  fall within 0.8 to 1.25. CCI

Additional PK analyses may be conducted if deemed appropriate.

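### The stated 90% power is for one PK parameter; the bioequivalence rule needs three, and on the plan's inputs has about 83-88%

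*Protocol*

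**What the plan says.** Protocol Section 9.5 and SAP Section 7 make the same statement: "A sample size of 108 participants per treatment group will provide approximately 90% power" that the 90% CI for the geometric mean ratio of Cmax and AUC will lie within 0.8 to 1.25. The inputs are log-normal parameters, a CV for Cmax and AUC of "approximately 40% (based on previous trials"), a true ratio of 1.07 and equal CVs in the two groups. The target is that "approximately 216 participants (108 in the PFS [reference] group and 108 in the AI [test] group) complete the study". One CV, one ratio and one power are given. No correlation between parameters appears, and the power is not said to be either per parameter or joint.

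The decision rule is in SAP Section 9.3.2. The devices "will be considered bioequivalent if the 90% CIs of the ratio of geometric least squares means of" three named parameters lie inside the limits of 0.8 and 1.25. The parameters it names are the two AUCs, to infinity and to the last measurable concentration, and Cmax. All three are primary endpoints in both documents. Protocol Section 9.3.2.2 states the same rule for plural intervals, without naming the parameters in that sentence.

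**The concern.** When three intervals must all pass, the chance of success cannot exceed the chance that any one passes, and it is lower unless the parameters are almost perfectly correlated. A power calculation with one CV and one ratio describes one parameter. If that is where the 90% comes from, it is not the power of the study's own success criterion. A reader of Section 9.5 would put the risk of an inconclusive result at about 10% when, on the plan's inputs, it is higher. Requiring all three to pass does not inflate type I error, so only the stated power is at issue.

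**Working it through.** **Inputs from the documents.** 108 per arm, CV 40%, ratio 1.07 and limits 0.8 to 1.25 (Protocol 9.5); 90% CI, that is, two one-sided tests at 5% (SAP 9.3.2). The model has an intercept, device (1 df), location (2 df) and weight stratum (2 df), so the residual df are 216 − 6 = 210.

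**Step 1: reproduce the 90% for one parameter.**
- Log-scale SD = √ln(1 + 0.40²) = √0.1484 = 0.3853.
- SE of the log ratio = 0.3853 × √(2/108) = 0.0524.
- Distance from the true ratio to the upper limit = ln 1.25 − ln 1.07 = 0.2231 − 0.0677 = 0.1555, or 2.97 SE.
- Normal approximation: Φ(2.97 − 1.645) ≈ 90.7%. The lower limit is more than 5 SE away and costs essentially nothing.
- Integrating over the sampling distribution of the variance estimate gives 90.5%.

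The stated figure is therefore reproduced as power for a single parameter.

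**Step 2: power of the all-three rule.** The three log ratios were simulated as correlated normal estimates with a Wishart covariance estimate (400,000 draws per case). All three 90% CIs had to fall within the limits, with CV 40% and ratio 1.07 for each parameter. The documents give no correlations, so these are assumptions: 0.5 to 0.95 between Cmax and either AUC, and 0.99 between the two AUCs.

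| Assumed Cmax-AUC correlation | 0.5 | 0.8 | 0.9 | 0.95 |
|---|---|---|---|---|
| All three parameters | 83.3% | 85.6% | 86.9% | 87.9% |
| Cmax and one AUC only | 84% | 86% | 87% | 88% |

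The second row shows that the gap does not depend on the third parameter. Changing the AUC-AUC correlation to 0.95 or 0.999 moves the first row by about 1 point or less. All-three power reaches 90% on these inputs only with near-perfect correlation: it is 89.1% with every pair at 0.99 and 90.1% with every pair at 0.999.

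**Step 3: what could close the gap.** All-three power over the same correlation range:

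| Analysed per arm | Residual CV | All-three power |
|---|---|---|
| 108 | 40% | 83-88% |
| 112 | 40% | 85-89% |
| 120 | 40% | 87-91% |
| 108 | 38% | 87-91% |
| 108 | 36% | 90-93% |

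If 40% is a total CV, a residual CV of 38% requires weight and location to explain 1 − ln(1 + 0.38²)/ln(1 + 0.40²) = 9% of the log-scale variance. A residual CV of 36% requires 18%. The rows with more participants assume that all three parameters are available for everyone. Early dropouts may lack AUC(0-∞), so the real gain could be smaller.

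**The case against.** The strongest reply is that the documents never claim joint power. Section 9.5 speaks of one CI and one ratio, uses one CV and no correlation, and its arithmetic is right for what it computes. The size of the gap comes from correlations assumed in this review. At 0.9 to 0.95 it is only 2 to 3 points, which could pass as "approximately" in an approximate statement. It is also no larger than the effect of small changes in other inputs: at 108 per arm, a true ratio of 1.06 gives 88-91% and 1.08 gives 78-84%.

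The gap may also not arise in practice. For the CV, "The model will include delivery device, injection location, and weight stratification as fixed-effects", and Protocol Section 4.2 reports statistically significant body weight effects on PK and that "injection location has been observed to have an impact on bioavailability in some studies with mirikizumab". The 40% is not said to be a residual CV. For the numbers, the PK population is "All enrolled participants who receive a full dose of study intervention and have evaluable PK data", with no requirement to reach Day 85; "participants who do not complete PK sampling through Day 85 may be replaced"; and up to about 240 may be enrolled. Finally, text is redacted directly after the bioequivalence rule in the SAP.

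Much of this stands as a limit on size: the upper part of the 83-88% range may be the relevant one, and the shortfall may be recovered. It does not remove the point. The text names both Cmax and AUC and does not label the figure as per parameter. The 90% is tied to 108 per group, and neither route to recovery is claimed in the sample size section. Sensitivity to the true ratio runs in both directions and does not turn single-parameter power into joint power. The redaction leaves the three named parameters in place.

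**Conclusion.** The concern holds. The 90% is the power for one parameter (90.5%), while the study's rule requires three. On the plan's own inputs the rule has about 83% to 88% power, so the risk of not meeting it is about 12% to 17% rather than about 10%. This rests on three conditions: a Cmax-AUC correlation of 0.5 to 0.95 with the two AUCs correlated at about 0.99, 40% as the residual CV, and 108 analysed per arm. A smaller residual CV or more analysed participants would close or nearly close the gap, and the documents leave both open. The consequence is a modestly understated risk of an inconclusive result; the analysis and the validity of a positive conclusion are unaffected.

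**What to change.** Keep 108 per arm. In Protocol Section 9.5 and SAP Section 7:

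- Label the 90% as power for each parameter considered separately.
- Beside it, state the power that all three 90% CIs fall within 0.8 to 1.25, with its assumptions. This is either about 83-88% at CV 40% and 108 per arm, with the assumed correlations given, or the value obtained from the Cmax-AUC correlation and residual CV in the previous trials already cited for the 40%.

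The cost is one sentence in each of two sections and a slightly less favourable stated power. No participants are added, and the analysis model and decision rule do not change.
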